## **6.7. Study Completion**

Completion of the study is defined as the time when the last subject completes the EOS Visit, or when the last subject is considered lost to follow-up, withdraws consent, or dies.

## 7. STUDY ASSESSMENTS AND PROCEDURES

### 7.1. Demography and Medical History

Demographics characteristics will be obtained for each subject at the Screening Visit.

All CKD-related medical history and all other significant medical history will be recorded in the CRF beginning at the Screening Visit. Throughout the study, medical conditions that are still ongoing will be regularly updated in the CRF.

### 7.2. Clinical Evaluations

#### 7.2.1. Vital Signs

Vital signs to be measured include systolic/diastolic blood pressure, heart rate, respiration rate, and temperature. Blood pressure will be measured after the subject has rested in a sitting position for a minimum of 5 minutes. At the Pre-Biopsy Visit (Day -3 to Day-1) and Pre-Injection Visit (Day -14 to Day -10 Visit), three BP measurements will be taken and the average of the 3 measurements (for systolic and diastolic pressure) used to satisfy entry criteria and entered into the CRF.

#### 7.2.2. Physical Examination

The Investigator or designee will perform the PE. The comprehensive examination will assess all pertinent body systems while the interim examination will include specific assessments of those body systems deemed appropriate for that subject by the Investigator. As a general rule for the interim examination, the Investigator will review the subject's AEs prior to, or in conjunction with, the examination and include assessment of related body systems as appropriate. Only clinically significant abnormalities will be recorded in the CRF.

The subject's weight will be measured at every visit that includes a complete or interim physical examination. The subject's height will be taken at the Screening Visit. Body Mass Index (BMI) will be calculated as kg/m^2.

#### 7.2.3. ECG

A 12-lead ECG will be obtained after the subject has been resting on their back for 5 minutes.

#### 7.2.4. Concomitant Medications

Concomitant medications will be recorded in the CRF as follows:

- **Screening Visit until first REACT injection:** Record any CKD-specific medications as well as medications that may affect renal hemodynamics and/or serum creatinine measurements. In addition, record any medications used to treat an AE that is documented in the CRF. Surgical medications used during the biopsy procedure do not need to be captured in the CRF unless their use falls outside of expected dosages and/or frequencies of administration.
- **First REACT injection until 6 to 7 months of follow-up:** Record any medications taken until 6 to 7 months after treatment, depending on when the second REACT injection will be administered. Surgical medications used during the REACT injection procedure do not need to be captured in the CRF unless their use falls outside of expected dosages and/or frequencies of administration.

- **Second (Final) REACT injection until 6 months of follow-up:** Record any medications taken until 6 months after the last REACT treatment. Surgical medications used during the REACT injection procedure do not need to be captured in the CRF unless their use falls outside of expected dosages and/or frequencies of administration.
- **6 months of follow-up through the EOS Visit:** Record CKD-specific medications, that may affect renal hemodynamics and medications that may affect serum creatinine measurements. Record medications used to treat any AE documented in the CRF.

#### 7.2.5. Funduscopic Exam of Retina

This exam should be completed at screening, month 12, and month 24/EOS to monitor for diabetic retinopathy of both eyes. Retinal photography should be collected and kept within the patient records and any worsening from baseline should be reported as an AE if not already documented in medical history.

### 7.3. Laboratory Assessments

Planned clinical laboratory evaluations are listed in [Table 12](#). Analyses will be conducted by a central laboratory, except as noted. The schedule for collecting biological samples during the study are shown in [Table 2](#).

**Table 12: Clinical Laboratory Evaluations**

Clinical Chemistry	Hematology	Urinalysis (24hr and Urine Chemistry)
Alkaline phosphatase ALT AST $\beta$ 2-Microglobulin Bilirubin Creatinine kinase FSH (females only) GGT $HbA_1c$ LDH PTH (intact)	Hematocrit Hemoglobin RBC count & indices WBC count & differential Pregnancy hCG (serum) – confirmatory	Albumin $\beta$ 2-Microglobulin Creatinine Protein Protein & Albumin:Creatinine Ratio NGAL
	Serology	Standard Panel
	HBV HCV HIV	pH Ketones Protein Blood Glucose Microscopic analysis
Renal Analytes	Coagulation Status	Drug Screen
Albumin BUN Calcium $CO_2$ , total Creatinine Cystatin-C CRP eGFR (calculated) Glucose Phosphorus Potassium Sodium	APTT PT-INR Platelet count Lipid Panel Cholesterol LDL HDL LDL:HDL ratio Triglycerides	Amphetamine Barbiturates Benzodiazepines Cocaine Opiates Tetrahydrocannabinol Phencyclidine

Abbreviations: ALT (Alanine Aminotransferase); APTT (Activated Partial Thromboplastin Time); AST (Aspartate Aminotransferase); BUN (Blood Urea Nitrogen); CRP (C-Reactive Protein); FSH (Follicle-Stimulating Hormone); GGT (gamma-glutamyl transferase);  $HbA_1c$  (glycosylated hemoglobin); HBV (Hepatitis B Virus); hCG (Human Chorionic Gonadotropin); HCV (Hepatitis C Virus); HDL (High Density Lipoprotein); HIV (Human Immunodeficiency Virus); LDL (Low Density Lipoprotein); NGAL (Neutrophil Gelatinase-Associated Lipocalin); iPTH (Parathyroid Hormone, intact); PT-INR (Prothrombin Time- International Normalized Ratio).

### 7.3.1. eGFR

GFR will be estimated using the Chronic Kidney Disease Epidemiology Collaboration (CKD-EPI) equation that incorporates both serum creatinine and Cystatin C. The specific assay for measuring creatinine will be defined by ProKidney, and the samples will be analyzed by the central laboratory. For comparison to each subject's historical values, it may be necessary to perform a second analysis at the site laboratory used to generate the historical data. The need for any additional assays conducted locally by the site laboratory will be defined at the Site Initiation Visit.

### 7.3.2. Urine Collection

Urine will be collected and analyzed via standard panel and urine chemistry. The schedules for collecting each type of urine sample are shown in [Table 2](#).

Urine will be collected over two different time periods: 24-hour collection and “spot” urine. Spot urine collections will be used for dipstick urinalysis (test stick) assessments. The schedules for collecting each type of urine sample are shown in Table 2. To provide a comprehensive picture of protein and albumin excretion, both total protein and albumin will be assessed in all samples.

### 7.3.3. Hematology

Hemorrhage following biopsy and REACT injection is a known and foreseeable risk to subjects participating in this study. Therefore, hemoglobin and hematocrit will be measured by the site's local laboratory before and after each procedure and compared to baseline levels. Other bleeding parameters (e.g., APTT, PTT-INR, platelets) also will be measured throughout the study.

### 7.3.4. Virus Serology

The biopsy cores obtained from each subject will be used for the expansion and selection of SRC. Contamination with HIV, HBV, and/or HCV would prevent ProKidney from manufacturing REACT product for that subject. Therefore, each subject will undergo testing for viral blood-borne pathogens, including HIV, HBV, and HCV.

### 7.3.5. Drug Screen

Consistent with Exclusion Criterion #24 (See [Section 5.2](#)), subjects are not eligible to participate in the study if they have an "...active history of ... drug abuse that, in the judgment of the Investigator, would impair the subject's ability to comply with the protocol." Therefore, subjects will undergo testing for drugs of abuse.

### 7.3.6. Pregnancy Screen

A qualitative urine pregnancy test will be performed at the site using a test-strip. If the test is positive, then a confirmatory test will be performed by the clinical laboratory. If site practices do not accept the results of a test-strip, then a urine sample should be sent to the central laboratory for analysis. Post-menopausal women with a confirmatory FSH test do not have to undergo pregnancy testing throughout the study.

### 7.3.7. Research Samples

Research samples (serum/plasma and urine) will be collected, frozen, and stored for the evaluation of novel biomarkers. Participating subjects can opt out of long-term storage of their unused specimens during the informed consent process or at any time during the study ([Section 3.5.2.2](#)).

## 7.4. Renal Imaging

### 7.4.1. Ultrasound

Renal ultrasound will be performed at the Screening Visit to verify subject eligibility (i.e., no evidence of renal tumors, polycystic kidney disease, renal cysts or other anatomic abnormalities that would interfere with the REACT injection procedure) along with obtaining a baseline echogenicity reading. Ultrasound will also be performed following the in-patient renal biopsy on Day 0 and Day 1 and following the in-patient REACT injection(s) on Day 0 and Day 1 with the aim of monitoring possible, subclinical AEs. Findings from the ultrasound (e.g., resistance index, length, etc.) will be recorded on the CRF. An ultrasound may be conducted at other times, in the judgment of the Investigator, if needed for additional safety evaluation(s).

### 7.4.2. Computerized Tomography

Computerized tomography (CT) must be used in conjunction with ultrasound during the REACT injection procedure, according to the usual standards of care at the investigative site. Use of fluoroscopic CT may be used in conjunction with ultrasound.

#### 7.4.3. Magnetic Resonance Imaging

An MRI study without contrast will be performed from the Screening Visit through Day -1 before renal biopsy to determine kidney size and volume. During the site initiation visit, the MRI process will be defined for each site, depending on the MRI equipment available. Generally, a 1.5-T unit should be used. MRI imaging studies will help determine kidney volume (for dosing calculations). MRI will be performed using standard sequences *without injection of contrast agents*. Renal volume measurements may be calculated, for example, using a fast 3D gradient-echo sequence, VIBE, with an acquisition time of 22 seconds and spatial resolution of 2 x 1.4 x 1.2 mm. Imaging parameters will be recorded in the source documents and CRF. A total of two MRIs will be performed on patients.

#### 7.4.4. Renal Scintigraphy

Renal scintigraphy will be used to assess left and right kidney function using the radioactive tracer  $^{99m}\text{Tc}$ -dimercaptosuccinic acid (DMSA) or  $^{99m}\text{Tc}$ MAG3 (Mercaptoacetyl triglycine). This method is considered as the most reliable for measuring renal cortical function and is the preferred agent for this clinical trial. If the site standard practice is to use a radiopharmaceutical other than  $^{99m}\text{Tc}$ -DMSA or  $^{99m}\text{Tc}$ MAG3 then the site must discuss their procedure with ProKidney or the Medical Monitor prior to site initiation. If the site's standard practice is considered sufficiently equivalent to the procedure using  $^{99m}\text{Tc}$ -DMSA or  $^{99m}\text{Tc}$ MAG3, then the site will be allowed to follow their procedure. In this case, a copy of the site's procedure will be signed/dated by the Project Leader from ProKidney and maintained in the site's regulatory binder. All patients in this study will receive five renal scintigraphy studies. Renal scintigraphy will be performed before the first REACT injection, before the last REACT injection, at the 6-Month Visit after the last REACT injection, at the 12-Month Visit after the last REACT injection, and at the EOS Visit for all patients.

### 7.5. Surgical Procedures

#### 7.5.1. Biopsy

Renal biopsy will be performed under sterile conditions using an ultrasound- or CT-guided approach consistent with site practices. Two biopsy cores will be needed to provide sufficient material for the selection of SRC and manufacture of REACT. Likewise, a 16-gauge needle should be used to insure adequate cortical material is obtained. If required, a 15-gauge needle may be used following consultation with the Medical Monitor and Manufacturing Facility. Bedside examination of the biopsy cores may be performed, if available, to ensure sufficient cortical material has been obtained.

Since the biopsy tissue will be used to manufacture REACT, the site must ensure that the tissue cores are harvested using sterile conditions so that the risk of contamination during subsequent cell expansion and selection is minimized. Contamination of the tissue cores could significantly jeopardize the ability of ProKidney to manufacture REACT product for that subject.

Guidance on wound care and pain management following the biopsy procedure will be provided in the Interventional Radiologist Manual. Briefly, the subject will remain supine for 4 hours with monitoring of hemoglobin, blood pressure, gross hematuria, abdominal/flank pain, and flank ecchymosis. As long as any biopsy-related AEs have resolved, stabilized, or returned to baseline, the subject can be discharged from the hospital on the day after the biopsy consistent with site standard practice. Importantly, any pain medication administered after the renal biopsy should be selected carefully, avoiding medications with nephrotoxic potential.

If a subject experiences significant AEs following the biopsy that, in the opinion of the Investigator, would put the subject at increased risk for significant adverse effects following REACT injection, then he/she will not be treated with REACT but will be followed until resolution of the event(s) and then discontinued from the study.

### 7.5.2. REACT Injection

Before performing the REACT injection, the operating physician will evaluate the subject as follows:

- Perform a physical examination to determine the feasibility of the procedure.
- Evaluate bleeding parameters, including coagulation panel, PTT-INR, platelets, hemoglobin, hematocrit, and other pertinent laboratory studies.
  - *Note: Hemorrhage following REACT injection is a known and foreseeable risk to subjects participating in this study. Therefore, hemoglobin and hematocrit will be measured before and after each REACT injection per the site's standard practice and compared to baseline levels.*
- Review imaging studies, including ultrasound, MRI, and CT or fluoroscopic CT, to determine route of access, depth of kidney, and appearance of cortical-medullary junction.
- Map potential REACT cell deposition sites.
- Determine classification and associated perioperative /post-operative risk according to the American Society of Anesthesiologists (ASA) with respect to airway assessment, medical history, allergies, and medications.
- Interview the subject and the subject's family/supporters to discuss the procedure, its risks and possible complications. Answer questions and obtain written informed consent.

Prophylactic antibiotics will be given intravenously according to site standard practice. An initial CT scan may be ordered, if necessary, to evaluate adjacent viscera, renal location, and the presence of renal cysts. A CT scan must be used in conjunction with ultrasound to locate the cortical-medullary junction.

REACT is targeted for injection into the kidney cortex via a needle/cannula and syringe compatible with cell delivery. The intent is to introduce REACT via penetration of the kidney capsule and deposit REACT into multiple sites of the kidney cortex. Initially, the kidney capsule will be pierced using a 15- to 20-gauge trocar /access cannula inserted approximately 1 cm into the kidney cortex.

In the Phase 1 clinical study, REACT was administered via an 18-gauge needle. The proposed Phase 2 study will utilize an 18-gauge or smaller needle for REACT delivery. The needle will be threaded inside the access cannula and advanced into the kidney, from which the REACT will be administered. Injection of the REACT will be at a rate of 1 to 2 mL/min. After each 1-to-2-minute injection, the inner needle will be retracted along the needle course within the cortex to the second site of injection, and so forth, until the needle tip reaches the end of the access cannula or until the entire REACT product has been injected. Using a percutaneous delivery approach, placement of the access cannula /trocar and delivery needle will be performed using direct, real-time imaging. A CT scan must be used in conjunction with ultrasound for the REACT injection procedure.

During the procedure, moderate conscious sedation will be employed; vital signs will be measured continuously. REACT injection will cease if there is imaging evidence of cell extravasation into

central or peripheral renal blood vessels, the medullary portion of the kidney, or through the renal cortex and into the retroperitoneal soft tissues, or evidence of active bleeding.

Following completion of the REACT injection, the inner needle will be withdrawn, and the outer cannula will remain in place for track embolization. During removal of the outer cannula (trocar), the site of the renal cortex puncture and needle track through the retroperitoneum will be embolized with absorbable gelatin particle/pledgets (e.g., Gelfoam® [Pfizer]) or fibrin sealant (e.g., TISSEEL [Baxter]) or other suitable agent to prevent excessive renal bleeding.

Upon completion of the procedure, non-contrast CT scan or ultrasound with color Doppler evaluation will be performed to image puncture site cell injection and any hematoma or bleeding events. The subject will be monitored for 2 to 3 hours post-procedure in a recovery-room environment with nursing assessment and measurement of vital signs. Subjects who do not experience complications may be discharged the same day as REACT injection, consistent with site standard practice.

## 8. SAFETY ASSESSMENTS AND MANAGEMENT

### 8.1. Adverse and Serious Adverse Events

#### 8.1.1. Definition of Adverse Events

An AE is the development of an undesirable medical condition (including abnormal laboratory findings) or the deterioration of a pre-existing medical condition following or during exposure to a study treatment, whether or not considered to have a causal relationship with study procedures or the investigational product. A pre-existing condition is a clinical condition (including a condition being treated) that is diagnosed before the subject signs the Informed Consent Form and is documented as part of the subject's medical history. Pre-existing conditions that are stable or unchanged should not be considered AEs.

The Investigator is responsible for ensuring that all AEs observed by the Investigator or reported by the subject that occur from the day of the biopsy procedure through 24 months after the final injection of REACT are monitored and recorded in the subject's medical record as well as the CRF provided by the Sponsor or its designee.

Treatment-emergent adverse events (TEAEs) are defined as any AE that started after the first injection of REACT or started prior to the first injection but increased in severity or frequency after the first injection of REACT.

Unscheduled visits may be performed at any time during the study as judged necessary by the Investigator to assess and conduct follow-up on AEs. Evaluations and procedures to be performed at unscheduled visits will be at the Investigator's discretion in consultation with the Sponsor and may be based on those listed in the Schedule of Events.

The Investigator's clinical judgment is used to determine whether a subject is to be removed from treatment due to an AE.

An AE is considered unexpected if it is not consistent in nature or severity with information contained in the current version of the **Investigator's Brochure** provided by the Sponsor.

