**Table 1: Time and Events Table**

Abbreviations: AE (adverse event); ConMeds (concomitant medications); DSMB (Data Safety and Monitoring Board); ECG (electrocardiogram); EOS (End-of-Study Visit); I /E (inclusion /exclusion); KDQOL (Kidney Disease Quality of Life Survey); MRI (magnetic resonance imaging); REACT (Renal Autologous Cell Therapy); PE (physical examination).

Notes:

- \* Day 1 follow-up visit should only be conducted if there is a safety event identified during or after the kidney biopsy.
- \*\* Every attempt should be made to ensure the second REACT injection is administered 6 months (+4 weeks) after the first injection. In the event that the subject cannot schedule his/her second REACT injection 6 months after receiving the first injection or cannot keep his/her scheduled 6-month visit, ProKidney and the Medical Monitor must be notified immediately. The expectation is that the subject and the clinical center will accommodate the Sponsor's preference that the series of 2 REACT injections should be administered no more than 6 months apart.
- a. If the screening assessment falls outside of the 60-day window before renal biopsy, re-screening will be performed as described in Screening ([Section 6.1](#)).
- b. Because the second REACT injection will occur 6 months (+4 weeks) after the first injection, the 6-month visit may not be scheduled.
- c. In the event that a second REACT injection will not be administered, the subject will undergo all follow-up assessments after the last REACT injection at the 24-month EOS Visit.
- d. The EOS Visit will take place 24 months after the last REACT injection, or when the subject is terminated from the study by the Investigator ([Section 8.6](#)) or when the subject voluntarily discontinues from the study ([Section 5.4](#)).
- e. The Informed Consent Form must be signed and dated prior to conducting any study-specific procedures, including those at the Screening Visit. Signing the Informed Consent Form starts the 60-day timeline for screening.
- f. The PE and interim PE are described in [Section 7.2.2](#).
- g. Vital signs include heart rate, resting blood pressure, respiration rate, and body temperature. ([Section 7.2.1](#)). At the Pre-Biopsy Visit (Day -3 to Day -1) and the Pre-Injection Visit (Day -14 to Day -10) three BP measurements will be taken and the average will be used to satisfy entry criteria.

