## 5. STUDY POPULATION

### 5.1. Subject Inclusion Criteria

Unless otherwise noted, subjects must satisfy each inclusion criterion to participate in the study. Inclusion criteria will be assessed at the Screening Visit, prior to renal biopsy, and before each REACT injection unless otherwise specified.

1. The subject is male or female, 30 to 65 years of age on the date of informed consent.
2. The subject has an established diagnosis of T2DM.
3. The subject has an established diagnosis of diabetic nephropathy as the underlying cause of renal disease.
4. The subject has an established diagnosis of CKD not requiring renal dialysis, defined as having an eGFR between 14 and 20 mL/min/1.73m^2 inclusive at the Screening Visit and prior to REACT injection.
5. The subject has blood pressure less than 150/90 at the Screening Visit, prior to renal biopsy, and prior to REACT injection(s). At the time of the biopsy and injections, the subject's BP should not be significantly below the previously recorded stable pressure.
6. The subject has stable blood pressure and is maintained on a stable anti-hypertensive medication regimen, if treatment for hypertension is necessary. If treatment includes an angiotensin-converting-enzyme inhibitor (ACEI) or an angiotensin receptor blocker (ARB), that treatment must have been initiated at least 8 weeks prior to renal biopsy. Treatment must be stable during the 6-week period immediately prior to REACT injection. Stable treatment is defined as dose adjustment to no less than one half of the current dosage or to no more than 2 times the current dosage. Dose interruptions up to 7 days due to medical necessity are allowed.
7. A minimum of 3 measurements of eGFR or sCr should be obtained at least 3 months apart prior to the Screening Visit or within the previous 24 months to define the rate of progression of CKD. The subject should have adequate, historical clinical data to provide a reasonable estimate of the rate of progression of CKD. The Medical Monitor may be consulted to ensure there is sufficient data.
8. The subject is willing and able to refrain from NSAID consumption (including aspirin) as well as clopidogrel, prasugrel, or other platelet inhibitors during the period beginning 7 days before through 7 days after both the renal biopsy and REACT injection(s).

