#### 8.1.1.1. Definition of Serious Adverse Events

An SAE is an AE that occurs during any phase of the study (i.e., baseline, treatment, washout, or follow-up) at any dose of the investigational product, comparator, or placebo, and fulfills one or more of the following:

- Results in death
- It is immediately life-threatening
- It requires in-patient hospitalization or prolongation of existing hospitalization
- It results in persistent or significant disability or incapacity
- Results in a congenital abnormality or birth defect
- It is an important medical event that may jeopardize the subject or may require medical intervention to prevent one of the outcomes listed above.

All SAEs that occur from the day of the biopsy procedure, during treatment, or within 24 months following the final REACT injection, whether or not they are related to study procedures or the

investigational product, must be recorded in the subject's medical record as well as the CRF provided by the Sponsor or its designee.

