4.9 Analysis Periods

The following analysis periods will be defined as:

- Pre-Injection Period: from the start day of biopsy to the first REACT injection.
- Acute First Injection Period: from the first REACT injection to 1 month following the first REACT injection. The acute first injection period is a subset of the inter-injection period defined below.
- Inter-Injection Period: from the first REACT injection to either the second REACT injection or (if no such second injection was delivered) trial withdrawal or completion.
- Acute Second Injection Period: from the second REACT injection to 1 month following the second REACT injection. The acute second injection period is a subset of the post-second-injection period defined below.
- Post-Second Injection Period: from the second REACT injection to trial withdrawal or completion. This period will not apply to participants for whom only one REACT injection was delivered.
- Post-Injection Period: from the first REACT injection to trial withdrawal or completion. This period includes both the inter-injection and post-second injection periods.

[figure not shown]
If necessary, imputed dates will be used to determine the analysis period for adverse events.

Figure 1. Analysis Period Diagram for Subjects that Received Two Injections

Abbreviations: EOS = End of Study

Figure 2. Analysis Period Diagram for Subjects that Received One Injection

Abbreviations: EOS = End of Study

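### AE and SAE recording starts on the day of biopsy, so study-caused events before it, including any from the required 7-day platelet-inhibitor withholding, have no recording rule

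*Protocol*

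**What the plan says.** **Recording window.** Protocol 8.1.1 covers AEs that "occur from the day of the biopsy procedure through 24 months after the final injection of REACT are monitored and recorded". Protocol 8.1.1.1 sets the same start for serious events: "All SAEs that occur from the day of the biopsy procedure, during treatment, or within 24 months following the final REACT injection" go into the medical record and CRF, related or not. SAP 7.2 and 7.2.4 repeat both rules. The earliest analysis period in SAP 4.9 matches: "Pre-Injection Period: from the start day of biopsy to the first REACT injection".

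**Definitions.** Under Protocol 8.1.1 a pre-existing condition is one that "is diagnosed before the subject signs the Informed Consent Form and is documented as part of the subject's medical history". Protocol 8.1.1.1 defines seriousness more widely than it records it: "An SAE is an AE that occurs during any phase of the study (i.e., baseline, treatment, washout, or follow-up").

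**What the study requires before biopsy.**
- Inclusion criterion 8 covers NSAIDs including aspirin, clopidogrel, prasugrel and other platelet inhibitors. Criterion 9 covers fish oil and platelet aggregation inhibitors such as dipyridamole. Both are to be avoided "during the period beginning 7 days before through 7 days after both the renal biopsy and REACT injection(s"). Section 5.3 repeats the prohibition.
- Section 5.3 also lets aspirin up to 100 mg/day continue under stated conditions. Criterion 8 has no such exception.
- Table 1, note e: "Signing the Informed Consent Form starts the 60-day timeline for screening". Section 6.1 allows a later biopsy by case-by-case agreement.

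**Status before biopsy.** Subjects are enrolled immediately before biopsy (protocol synopsis, SAP 3.1) or once it is taken (SAP 4.2). A subject who withdraws earlier is a screen failure (Protocol 5.4).

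**The concern.** The primary endpoint is AEs related to the procedure and/or the product (Protocol 2.1). If a subject stops a platelet inhibitor only because a study biopsy is planned, harm from stopping it is a consequence of that procedure. As written, a thrombotic event in that week carries no AE or SAE recording duty and belongs to no SAP analysis period. The same holds for harm from another study-required screening procedure. If the event prevents the biopsy, the subject leaves as a screen failure, outside both analysis sets.

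Relatedness has a matching gap. Protocol 8.2.2 asks about the study procedure or the investigational product, and SAP 7.2.3 about the biopsy, the injection procedure or the product. Neither says where a required medication interruption belongs.

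**Working it through.** The plan gives no figure to reproduce: it is descriptive, with up to 10 subjects. The check is a timeline and a day count.

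**1. Which withholding falls outside recording?** There are three procedures: the biopsy and two injections.
- Pre-procedure withholding: 3 × 7 = 21 days.
- The 7 days before biopsy precede the window.
- The first injection is planned about one month after biopsy (Protocol 4.5, 6.2). Its 7-day period therefore starts about 30.4 − 7 = 23.4 days after biopsy, inside the window. The period before the second injection is later still.
- All post-procedure withholding is inside.
- Outside recording: 7 of 21 days, one period in three.

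**2. How much time is that?**
- Withholding: 10 × 7 = 70 subject-days at most, if every subject takes a drug that must be stopped. The documents do not give the proportion who do.
- Consent to biopsy: 10 × 60 = 600 subject-days at most, or 600/365.25 = 1.64 person-years. Taking the 31-month duration as running from biopsy, this is 60/(60 + 31 × 30.44) = 6.0% of planned time from consent to end of study.
- These totals are for 10 biopsied subjects. Subjects screened but never biopsied would add time; their number is not stated.

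**3. How is an event in that interval classified?** Take a new event 3 days before biopsy in a subject who has stopped clopidogrel as required.
- Pre-existing? No. It was diagnosed after consent.
- Within AE or SAE recording? No. That starts on the day of biopsy.
- Within the wording of the SAE definition? Yes, if serious, because that names baseline.
- In an SAP analysis period? No. The first starts at biopsy.

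**4. Does another section close the gap?** Not in the text available.
- Protocol 8.3 sets a 24-hour clock for reporting SAEs but gives no start date.
- Protocol 7.1 collects significant medical history from screening, which does not feed the AE tables.
- Protocol 7.2.4 asks, from screening, for medications used for AEs already in the CRF. It presupposes such AEs without requiring their entry.

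**5. Illustration only.** The documents give no event risk. With k subjects exposed and an assumed risk p for each, the chance of at least one unrecorded event is 1 − (1 − p)^k.
- k = 10: 9.6% at p = 1%, 18.3% at 2%, 40.1% at 5%.
- k = 3: 3.0%, 5.9% and 14.3%.

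**6. Subjects biopsied under RMCL-002.** Protocol 5.4 admits them without a new biopsy. Their recording start is undefined here: read literally, it is a biopsy done in another study.

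**The case against.** Much of the case on the other side stands, and it limits the point.

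- **Aspirin.** A reader might infer that every subject must stop aspirin. Section 5.3 does not support that: it conditionally allows up to 100 mg/day for subjects with diabetes who are over 40 or have added cardiovascular or stroke risk. The point rests on the drugs without an exception.
- **Effect on reported rates.** A reader might infer that one missed event shifts an incidence by 10 percentage points. It does not. A subject never biopsied is outside the FAS (SAP 4.2), and a pre-biopsy event in a treated subject is not a TEAE unless it worsens after the first injection.
- **Events lost altogether.** That is also too strong. A CRF exists for every consented subject with one study-specific assessment (Protocol 11.1.1), and an event may surface through medical history or SAE reporting. What is missing is the duty to record it as an AE or SAE. The grid of Table 1 could not be seen, so its AE row is unchecked.
- **Definition wording.** The AE definition refers to exposure to a study treatment, an SAE must first be an AE, and the SAE text is generic: it mentions a comparator and placebo that this study lacks. So the mismatch may be loose drafting. But the protocol does not apply the exposure condition strictly either, since it records AEs from biopsy, about a month before any REACT is given.
- **The 60 days.** Most of this interval involves neither biopsy, REACT nor required withholding. Collecting every minor event in it would be a preference, so the case for non-serious AEs is confined to those attributed to something the study required.

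**Conclusion.** The point holds in a narrow form. The written recording window opens after the study has begun to impose risk. An event from required withholding, or from another study-required screening procedure, is neither pre-existing nor recordable, and the SAE definition and SAE window in Protocol 8.1.1.1 do not agree. The withholding gap is at most 7 days per subject who takes such a drug, up to 70 subject-days in 10 subjects. This rests on the text alone, with the Table 1 grid unseen and the use of these drugs unknown.

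It is a cheap improvement to consider. It does not undermine the TEAE analyses.

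One related wording needs attention. The death trigger in Protocol 8.6 refers to enrolled subjects, which leaves a death between consent and biopsy outside that item. A reader might infer that no listed trigger could apply; that is not supported, because the item on severe or life-threatening related SAEs is not limited to enrolled subjects. The sponsor should reconcile the wording of 8.6 with the SAE definition. No new stopping rule is proposed here.

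**What to change.** - **Protocol 8.1.1 and 8.1.1.1, with SAP 7.2 and 7.2.4:** from informed consent, record all SAEs and any AE attributed to a protocol-required procedure or medication interruption. Leave other AEs on the present window. This also gives a defined start for subjects biopsied under RMCL-002.
- **Protocol 8.2.2 and SAP 7.2.3:** state that a required medication interruption counts as a study procedure for relatedness. This may bear on how the existing triggers in 8.6 are read, so settle it together with the wording of 8.6.
- **SAP 4.9:** add a consent-to-biopsy period, listed and tabulated separately for all consented subjects. Do not count its events as TEAEs, except where the existing definition already applies because an event worsens after the first injection.
- **Inclusion criterion 8 and Protocol 5.3:** reconcile the two statements on aspirin.

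The cost is a protocol clarification, one CRF instruction, and one extra listing and table. The CRF is already required for these subjects, SAP 5.1 already lists all screened subjects, and the TEAE definition and tables stay as planned. The downside is a few background SAEs from subjects who later fail screening; separate tabulation keeps them out of the treatment results.
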